The overall purpose of this protocol is to assess the biomechanical and neurophysiologic effects of rehabilitative strategies and protocols that are commonly used during physical therapy treatment of gait disorders post-stroke. As part of this protocol, 45 able-bodied individuals and 55 individuals with chronic stroke will be assigned to either Cohort 1 or Cohort 2, and will participate in 1-18 gait training sessions. If interested, study participants can also complete both study cohorts sequentially (with at least 3-weeks duration between switching from one cohort to the second). Evaluations for obtaining outcome measures will comprise clinical testing, muscle evaluations, gait analysis, and assessment of spinal and corticospinal excitability. Within Cohort 1 (stroke and able-bodied), 25 subjects will receive identical treatment throughout the training sessions (i.e. FastFES training). Within Cohort 2, 25 subjects will receive different rehabilitation strategies individually or in combination during each training session (e.g., treadmill walking, functional electrical stimulation, bio-feedback or verbal feedback about targeted walking parameters, split-belt walking, etc.). During gait training, Cohort 1 subjects will typically participate in a minimum of 2 and a maximum of 3 sessions per week. Subjects in Cohort 2 can participate in 1 to 18 gait training sessions but the frequency of the gait sessions can be varied according to the subject's and laboratory schedule (i.e. variable durations between consecutive sessions).

Aims

The aims of this protocol are to:

- 1) Study the changes in gait biomechanics, corticospinal excitability, and walking function during 18 sessions of gait retraining (Cohort 1).
- 2) Systematically determine the effect of parameters such as walking speed (slow, fast, variable, split-belt walking), functional electrical stimulation parameters (short-term changes induced by fast versus FastFES, stimulation intensity, number of muscles stimulated), and bio-

[figure not shown]
feedback on within-session changes in gait biomechanics, walking function, and corticospinal excitability (Cohort 2).

Hypotheses of the study

- By utilizing data collected on cohort 1 of subjects who undergo 18 sessions of FastFES gait retraining, the following hypothesis will be tested:

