 - H1.* Eighteen sessions (6-8 weeks) of gait training comprising fast treadmill walking and functional electrical stimulation (FastFES) will result in Improvements in gait biomechanics, corticospinal excitability, and walking function.
 - H2.* Improvements in gait biomechanics will precede the improvements in corticospinal excitability and walking function.
 - H3.* Improvements in walking function will be correlated to improvements in corticospinal excitability.
- By utilizing data collected on cohort 2 of subjects who receive different rehabilitation strategies during each training session, we will analyze short-term changes induced by 1-3 sessions of gait retraining to test the following hypothesis:
 - H4.* The magnitude of improvements in gait biomechanics and corticospinal excitability will be greater for gait training sessions that comprise:
 - walking at a faster versus slower speed
 - walking with versus without FES, i.e. Fast versus FastFES
 - walking with FES delivered to two versus one muscle during gait
 - walking with 2 belts going at different speeds or directions versus regular treadmill walking
 - walking with versus without visual bio-feedback or other feedback (e.g. verbal, tactile) about targeted parameters during gait
 - greater dosages (# of walking steps per session) of walking practice
 - combination of 2 strategies versus a single rehabilitation strategy

5. Study design and methods

Research Procedures

Flowchart showing the overview of study procedures.

The overall goal of this protocol is to provide novel insights into the biomechanical and neural mechanisms underlying gait rehabilitation. To achieve this goal, a series of experiments will be performed on young able-bodied individuals as well as stroke survivors. The protocols to be tested and procedures to be used are described in detail here. For all the procedures and sessions described below, all testing procedures will be explained to the subject at the beginning of each testing session. Also,

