during these testing procedures, rest breaks will be provided to the subjects as needed and as requested by the subject. Please see the adjoining flowchart for a summary of the procedures that subjects in each study cohort will undergo. Subjects will not be randomized to the 2 cohorts. Assignment to the cohorts will be based on the lab/personnel and subject schedules. A subject can participate in the 2 cohorts sequentially. Also, participants in Cohort 2, when testing hypotheses comprising a repeated-measures comparison of different gait training strategies (e.g. Hypothesis 4a evaluating effect of walking speed; Hypothesis 4b comparing FastFES versus Fast), participants may cross-over between strategies within or across gait sessions.

1) Medical Clearance:

If a subject shows interest in participation in cohort 2 of the study (18 training sessions), before participation, we will obtain written medical clearance from the subject's physician (See attached Medical Clearance form). In addition, the subject will undergo clinical assessment to confirm that they are eligible for study participation.

2) Procedures for Clinical Assessment of Walking Function and Muscle Strength:

All subjects will review and sign consent forms before clinical testing. Clinical Testing will be performed by a licensed physical therapist. Clinical testing may comprise: (1) measurement of subjects' over ground self-selected (SS) walking speed (6-meter walk test); (2) over ground walking endurance measured by the distance ambulated during the 6-minute walk test; (3) assessment of gait and dynamic balance (measured using the functional gait assessment, 4-square step test, and the Berg balance score); (4) lower extremity portion of the Fugl-Meyer score⁷⁰; (5) step activity monitoring; (6) lower extremity proprioception (in which each limb segment will be flexed or extended approximately 10 degrees and the subject will be asked to identify whether the limb is moving and in what

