For gait training, as part of Cohort 1, the subject will receive the same type of walking training (fast treadmill walking with electrical stimulation) for all 18 sessions and participate in 2-3 training sessions per week over the course of 6-weeks. For cohort 1, the gait training sessions may comprise up to six 6-minute bouts of walking with rest breaks between bouts (total 30-minutes of walking). The last training bout (bout 6) may comprise 6-minutes of over ground walking (Fig. 1), during which subjects will be asked to walk as fast as they can. For safety, a physical therapist will walk with and guard the subject during over ground walking. For cohort 1, outcome measures may be obtained before, after, and intermittently throughout the 6-weeks of training (e.g. clinical testing, muscle strength testing, and assessment of corticospinal and spinal excitability).

Subjects in Cohort 2 will receive different types of walking training (e.g. treadmill walking at slow or fast speed, training with (FastFES) or without stimulation (Fast), training with or without feedback, etc.) for each of the training sessions, and will complete 1-3 training session per week with a variable delay (1-day to several weeks) between consecutive sessions. For cohort 2, outcome measures may be obtained before, after, and intermittently during each of the training sessions (e.g. clinical testing, muscle strength testing, and assessment of corticospinal and spinal excitability). For Cohort 2, when the subject receives different types of training during each of the 18 sessions, the training may comprise a total of 10 to 40-minutes of different types of walking. Depending on the gait training strategy being tested during the session, the session may comprise one or more of the following:

- Treadmill walking at a range of walking speeds (ranging from slower than comfortable self-selected speed to the subject's fast walking speed)
- Electrical stimulation applied to the ankle muscles at appropriate phases of the gait cycle during gait training
- Walking with both treadmill belts running at different speeds or directions
- Greater versus smaller dose of walking practice (three versus six 6-minute bouts)
- Bio-feedback, visual cues, or verbal / tactile cues regarding specific parameters of gait such as push-off forces, knee flexion angle during swing phase, etc.

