Hypotheses testing will be done with a p-value set at 0.05. The outcome variables used for analyses will include peak knee and ankle flexion during walking, propulsive forces during walking, walking speed and endurance, peak and duration of EMG activation during walking, and TMS-derived measures of corticospinal excitability (peak EMG in response to TMS, motor threshold intensity, slope and peak of the TMS-recruitment curve). To test *H1*, for each of the variables, one-way repeated measures ANOVA will be performed to check for differences in the variable after versus before 18 sessions of training. To test *H2*, we will plot the dependent variable versus time (test session number). Using these plots, the time to plateau and the time when the variable first shows a positive within-session change (threshold time) will be determined. One way repeated measures ANOVA will be used to compare the time to plateau and threshold time among 3 variables – peak propulsion, peak TMS muscle response, and over ground walking speed. To test *H3*, a Pearson's correlation will be performed between the change in peak propulsion after training versus change in peak TMS muscle response after training. For the hypothesis involving within-session changes (*H4*), repeated measures ANOVA will be performed to compare the within-session percentage change for each variable between different rehabilitation strategies.

Power Analysis: The current protocol has been powered using the primary outcome measure of paretic propulsive force generation. Based on means and standard deviations from our existing pilot data, for each aim, a sample of 24 subjects will provide 80% power to detect a 4.2% difference in propulsive force between sessions with standard deviation of 6% at a two-sided alpha level of 0.05. After completion, the data from this study will be used to conduct systematic power analysis for other outcome variables, which will be utilized to design a larger-scale future study.

8. Adverse event reporting

We will notify the IRB of any adverse events that occur during the protocol.

10. Device information

Equipment for Motion Analysis and Gait Retraining: A 7-camera system will be used to collect motion analysis data (Vicon, Oxford, UK). Ground reaction forces during treadmill walking will be collected using a treadmill instrumented with two 6-component force platforms under each

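### The repeated measures ANOVA for H4 has no place for partial or unequally repeated strategy sets, which Cohort 2 permits; the loss runs from negligible to large with an attendance pattern the plan does not state

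*Combined protocol and SAP*

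**What the plan says.** Section 7 (Statistical analysis) gives H4 one sentence: "repeated measures ANOVA will be performed to compare the within-session percentage change for each variable between different rehabilitation strategies". It does not say who enters each comparison, what minimum data a person needs, how several sessions of one strategy become one score, or what happens when a strategy is missing.

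The design text bearing on this is as follows.

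- Section 4 (Objectives): "Subjects in Cohort 2 can participate in 1 to 18 gait training sessions", at a frequency set by the subject's and laboratory's schedules.
- Section 4 (Hypotheses of the study): for H4, "we will analyze short-term changes induced by 1-3 sessions of gait retraining". Seven comparisons follow, most with two levels.
- Section 5 (Research Procedures): for repeated-measures comparisons such as 4a and 4b, "participants may cross-over between strategies within or across gait sessions".
- Section 5, item 8: the brain stimulation part is optional, although corticospinal excitability is an H4 outcome.

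Other text shows that comparison within persons is the intention. Section 4 states "Within Cohort 2, 25 subjects will receive different rehabilitation strategies individually or in combination during each training session", Section 5 item 4 states "Subjects in Cohort 2 will receive different types of walking training", and item 4 also describes 4b as a repeated-measures comparison.

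**The concern.** Classical repeated measures ANOVA works on a complete table of persons by strategies with one entry per cell. A person with two of three strategies leaves a three-strategy test altogether. A person with four sessions of one strategy and one of another has no defined entry. The protocol allows both situations without any dropout.

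Each H4 comparison could then rest on fewer people than the 24 in the power statement. Those people would be selected by which strategies they happened to receive, and the number could differ by outcome because TMS is optional. Section 5 item 4 says that the 4b data will inform sample-size estimation for a larger trial, so an undefined analysis set would carry forward.

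**Working it through.** **Inputs.** Section 7: "a sample of 24 subjects will provide 80% power to detect a 4.2% difference in propulsive force between sessions with standard deviation of 6" per cent, at a "two-sided alpha level of 0.05". Section 4: 25 people in Cohort 2. The documents do not give the number of strategies per person, so those patterns are assumptions.

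**The plan's own figure.** If 6% is the SD of the paired difference, n = (6 × (1.960 + 0.842) / 4.2)² = 16.02, so 17 people, or 19 with the t distribution. At n = 24 the t-based power is 91%, not 80%. A figure near 24 at 80% appears if 6% is a per-session SD with a between-session correlation of about 0.25 to 0.3. At 0.25 the paired SD is 6√(2 × 0.75) = 7.35 and n = (7.35 × 2.802 / 4.2)² ≈ 24. The plan does not say which SD is meant. I use 6% as the paired SD, the more favourable reading here.

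**Power by number of complete people** (SE = 6/√n, noncentral t):

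| Complete people | 25 | 24 | 20 | 18 | 12 | 10 | 8 |
|---|---|---|---|---|---|---|---|
| Power, paired SD 6% | 92% | 91% | 84% | 80% | 60% | 51% | 40% |
| Power, paired SD 7.35% | 78% | 77% | 68% | 63% | 44% | 37% | 29% |

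**How many could be complete.** Assume session counts spread evenly over the permitted range, one strategy per session and no cross-over within a session. The ranges run from strategies drawn at random to strategies never repeated.

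- 1 to 3 sessions, two strategies: (0 + 1/2 + 3/4)/3 = 42% to 2/3 = 67%.
- 1 to 3 sessions, three strategies in one ANOVA: (0 + 0 + 6/27)/3 = 7% to 1/3 = 33%.
- 1 to 3 sessions, four or more strategies in one ANOVA: none.
- 1 to 18 sessions, two strategies: 89% to 17/18 = 94%.

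**Mixed model on the same data, two-level contrast.** The residual variance is 6²/2 = 18. Let ρ be the share of variance between persons and v = 18/(1 − ρ). With c people having both sides and s people having one, split evenly, SE = [c/36 + s/(4v)]^(−1/2).

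- 90% complete (c = 22.5, s = 2.5): ANOVA SE = 6/√22.5 = 1.26. Mixed model: ρ = 0 gives (0.625 + 0.035)^(−1/2) = 1.23; ρ = 0.8 gives (0.625 + 0.007)^(−1/2) = 1.26.
- Half complete (c = s = 12.5): ANOVA SE = 6/√12.5 = 1.70. Mixed model: ρ = 0 gives (0.347 + 0.174)^(−1/2) = 1.39; ρ = 0.8 gives (0.347 + 0.035)^(−1/2) = 1.62.

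**Three strategies, with 1, 2 or 3 attended equally often.** Averaging over simulated attendance, about 8.4 of 25 people are complete and the ANOVA SE is 2.14. Pair by pair, (0 + 1/3 + 1)/3 = 44%, or about 11 people, have a given pair, and the SE is 1.83. The mixed-model SE is 1.48 at ρ = 0 and 1.67 at ρ = 0.8.

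**Power at 4.2%**, averaged over simulated attendance. Mixed-model ranges cover ρ from 0 to 0.8 and two choices of degrees of freedom: observations minus strategies, or observations minus participants minus strategies plus one.

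| Assumed pattern | Repeated measures ANOVA | Mixed model |
|---|---|---|
| Two strategies, 90% have both | about 88% | 89-92% |
| Two strategies, half have both | about 60% | 65-83% |
| Three strategies, one third complete | about 47% (55% pair by pair) | 67-79% |

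**Source of the gain.** As ρ approaches 1 the mixed model approaches the analysis with participant as a fixed effect. For a two-level contrast without repeats, that is the complete-pair analysis, so the whole gain is between-person information. In the three-strategy case the participant-fixed analysis still has SE 1.72 and power of 65-67%, so most of that gain needs no between-person information.

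**The case against.** The strongest reply is that the plan describes planned within-person comparisons. Participants are to receive different strategies, 4a and 4b are called repeated-measures comparisons, and H4 is a list of mostly two-level contrasts. If each contrast is run in people scheduled for both sides, the named method is standard and little is lost: with 24 of 25 complete, the SE is 1.225 against 1.216-1.222 for a mixed model. No passage specifies a three-strategy ANOVA. Analysis of complete pairs also protects against confounding between persons, because strategy exposure is not described as randomised.

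Much of this stands. It limits the size of the problem and gives the complete-pair analysis a real advantage. It does not remove the gap. Receiving different strategies does not guarantee both sides of a particular contrast, and someone with 1 to 3 sessions of one strategy each cannot cover most of the seven comparisons. Aim 2 lists four kinds of walking speed, so an analysis with more than two levels is not excluded either. The plan still has no rule for partial or repeated data.

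**Conclusion.** The mismatch is real: the named method requires complete, single-entry strategy sets, and the protocol permits incomplete and unequal ones without a rule. Its size cannot be fixed from the documents. Under the stated assumptions it runs from negligible (90% have both sides) through moderate (half do) to large (three strategies in one ANOVA, one third complete). If 6% is a per-session SD, there is less margin at every number of complete people.

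Three stronger readings are not supported.

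- A reader might infer that most of the data will be discarded. That needs a low-attendance pattern or several strategies in one ANOVA, and the documents establish neither.
- A reader might infer that a one-session participant always contributes nothing. Section 5 allows cross-over within a session and outcome measurement during it, so one session can hold both sides of a contrast.
- A reader might infer that the ANOVA loses precision for nothing in return. It avoids comparison between persons, which matters when exposure is not randomised.

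This is an inexpensive improvement to the analysis. It does not show that H4 cannot be tested.

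**What to change.** In Section 7, replace the H4 sentence with a linear mixed model on session-level scores, or on condition-level scores where strategies are crossed within a session. Include strategy and session order as fixed effects, participant as a random effect, and a participant-by-strategy random effect where strategies are repeated. State each H4 comparison as a contrast from that model and report, by outcome, how many participants received both sides.

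Alongside it, report the within-participant-only estimate with participant as a fixed effect. It uses every person with at least two of the modelled strategies and no between-person information. Say also whether the 6% SD is that of a session value or of a paired difference.

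The cost is wording; no new data or procedures are needed. The downside is that the mixed model assumes that which strategies a person received is unrelated to response. The within-participant estimate checks this, and a material difference between the two should be reported as such. With complete data the two analyses nearly coincide, so little is given up if attendance turns out well.

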Note that data from Cohort 1 (case series on FastFES gait training) as well as data that evaluate Hypothesis 4b (i.e. a repeated-measures comparison of the short-term effects of FastFES versus Fast on corticospinal excitability and gait biomechanics) will inform the methodology, planning, and sample-size estimation for a future larger clinical trial.

At the beginning and end of each training session, a “**pre-test**” and “**post-test**” may be performed. The pre- and post-tests will comprise 30-second trials of treadmill walking at the subject's comfortable or fast walking speed. By obtaining data while

training at a standardized walking speed and while training without FES, we will be able to measure differences in motor learning among these training strategies. The procedures for motion analyses to be used for pre- and post-tests are described in a separate section (Procedures for Motion Analyses). In addition, for a few sessions, in addition to the 30-second walking trials, the pre- and post-test may comprise assessment of spinal or corticospinal excitability.

During the training sessions, subjects may wear a harness suspended from the ceiling (no body-weight support) for safety. In addition, if needed, the subjects will be allowed to hold on to the hand rails during walking. For stroke survivors, heart rate will be monitored throughout the session with a heart rate sensor that is placed on the chest under clothing (Polar USA, Lake Success, NY). If heart rate exceeds 80% of their age predicted heart rate maximum, walking will be stopped until it returns to baseline. In addition, blood pressure will be monitored at each rest break. If a subject's blood pressure exceeds 190/100 mmHg, the session will be stopped and their blood pressure will be continually monitored until it returns to baseline. Subjects will rate their perceived exertion on the Borg Scale of Perceived Exertion every 6 minutes. If a subject reaches level 13 on the Borg scale (i.e. between 'Fairly Light' and 'Somewhat hard') they will be given a rest break⁷⁴.

5) Procedures for Motion Analysis:

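### The H4 analysis has no rule for a training session ended by the blood pressure limit; if its post-test is missing, repeated measures ANOVA also discards that participant's completed session

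*Combined protocol and SAP*

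**What the plan says.** All references are to the combined protocol and SAP.

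- **Analysis (Section 7).** For H4, "repeated measures ANOVA will be performed to compare the within-session percentage change for each variable between different rehabilitation strategies". The score needs a value before and a value after training in the same session.
- **Measurement (Section 5, item 4).** The pre-test and post-test are placed as follows: "At the beginning and end of each training session". The same sentence makes them optional. On content: "The pre- and post-tests will comprise 30-second trials of treadmill walking at the subject's comfortable or fast walking speed".
- **The rule that ends a session (Section 5, item 4, repeated under Risks).** The trigger and its consequence read: "blood pressure exceeds 190/100 mmHg, the session will be stopped and their blood pressure will be continually monitored until it returns to baseline".
- **The rules that do not end a session (Section 5, item 4).** For heart rate: "If heart rate exceeds 80% of their age predicted heart rate maximum, walking will be stopped until it returns to baseline". At level 13 on the Borg scale, "they will be given a rest break".
- **Design.** H4 (Section 4) predicts larger gains with, among others, faster walking, more steps, and two strategies rather than one. Section 5 lets Cohort 2 participants cross over between strategies, so these contrasts are within participant.
- **Loss.** Section 6 allows for about 10% withdrawal from the study. Nothing covers a lost session, a shortened session, a missing post-test or an analysis set.

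**The concern.** A score that depends on an end-of-session measurement sits beside a rule that can end the session early, and the plan does not connect the two. Either outcome of a stop causes a difficulty. If no post-test is taken, the within-session change is missing. If one is taken, it follows a shortened session that would still carry the label of the full strategy.

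In the first case the method adds to the loss. Conventional repeated measures ANOVA uses complete cases, so one unscored session removes the participant from the contrast and the usable session goes too. That is a property of the method, not something the plan states. The contrast then applies to people who tolerated both strategies. If those who are stopped would also have gained less from the harder strategy relative to the easier one, its advantage is overstated. Section 5, item 4, says the comparison of FastFES with Fast will inform the methods and sample size of a larger trial, so an error here could carry forward. With no rule written down, the handling would be chosen after the data are seen.

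**Working it through.** **1. The plan's own figure.** Section 7 gives 24 subjects per aim, 80% power, a 4.2% difference in propulsive force, SD 6% and two-sided alpha 0.05. Reading 6% as the SD of the paired difference:

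- standardised effect = 4.2 / 6 = 0.70; noncentrality = 0.70 × √24 = 3.43
- paired t-test power = 90.7%, not 80%; 19 subjects would give 82.2% and 18 would give 79.9%

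The stated 80% is recovered if the SD of the difference is 7.03% (4.2 / 7.03 = 0.597). The plan does not say which SD it means. That is a separate matter, so both readings are carried below.

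**2. Precision lost by dropping participants.** Let q be the share of participants with an unscored session in a two-strategy contrast. The documents give no value for q; it is an assumption.

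| q | Completers of 24 | Power if difference SD is 6% | Power if 24 gives exactly 80% |
|---|---|---|---|
| 0 | 24 | 90.7% | 80% |
| 5% | 23 | 89.4% | 78.1% |
| 10% | 22 | 87.9% | 76.1% |
| 20% | 19 | 82.3% | 69.2% |

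Cohort 2 is planned at 25 (Section 4), one more than 24.

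**3. Bias among completers.** Assume that those stopped are the lowest on a tolerance trait correlated r with the between-strategy difference, whose SD is 6%. The bias is r × 6 × φ(z) / (1 − q), where z is the q-quantile of the standard normal and φ its density.

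- r = 0: bias is zero at any q.
- q = 10%: φ(−1.282) / 0.90 = 0.1755 / 0.90 = 0.195. Bias = 0.3 × 6 × 0.195 = 0.35 points, or 0.5 × 6 × 0.195 = 0.59 points.
- Exactly one of 24 stopped: the expected lowest of 24 standard normal values is −1.948, so the mean of the other 23 shifts by 1.948 / 23 = 0.085. Bias = 0.3 × 6 × 0.085 = 0.15 points, or 0.5 × 6 × 0.085 = 0.25 points.

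For scale, the full-sample SE is 6 / √24 = 1.22 points.

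**4. Type I error.** Simulation of 200,000 null contrasts per setting, paired t-test on completers, nominal two-sided 5%:

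| Stopped | r = 0 | r = 0.3 | r = 0.5 |
|---|---|---|---|
| one of 24 | 5.0% | 5.3% | 5.8% |
| 10% | 5.0% | 5.8% | 7.3% |
| 20% | 5.0% | 7.3% | 11.7% |
| 30% | 5.0% | 9.1% | 17.5% |

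The last two rows need stop rates for which the documents offer no support.

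**5. Check of possible remedies.**

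- *Mixed model on all scored sessions.* In simulation it lowered the SE slightly. It cut the bias by about 15% to 35% when stopping tracked the strategy difference, and raised it when stopping tracked the harder session's own score.
- *Scoring every stop as zero and requiring significance to hold.* Assume a mean change of 5% in the easier session, a true difference of 4.2%, difference SD 6%, and 20% stopped at random. The expected contrast falls to 0.8 × 9.2 − 5 = 2.36, and power falls from about 91% to about 37%, although stopping is unrelated to benefit. That is too harsh to be a condition for supporting H4.

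**The case against.** The strongest reply is that most of the harm is conjecture. The plan never says that a stopped session lacks a post-test. It monitors blood pressure back to baseline and is silent on what follows. Section 5, item 4, also allows optional intermittent measurements during Cohort 2 sessions, and nothing rules out repeating a session. Stops may be rare: Section 6 screens resting heart rate, resting blood pressure and the ability to walk for 6 minutes, and fast speed is set from a 4-minute treadmill bout already completed (Section 5, item 2). The heart rate and Borg rules may interrupt effort before the blood pressure limit is reached.

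This stands, and it limits the point. A reader might infer three stronger claims that the documents do not support:

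- *Any safety rule removes the post-test.* Only the blood pressure rule ends a session. The other two pause walking or give a rest break; they can alter the session delivered but do not by themselves remove the post-test.
- *Stops will be commoner in the strategies that H4 favours.* This is plausible for speed and dose, but no rate by strategy is given, and it need not hold for the feedback, split-belt or stimulation contrasts.
- *H4 is therefore biased in its own favour.* Bias needs a link between stopping and the between-strategy difference, and none is documented.

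The reply does not remove the gap: no scoring rule exists, and the named method is the one that loses a completed session.

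**Conclusion.** The point holds as a gap in the analysis plan with a conditional consequence. The missing scoring rule is documented; the missing post-test, the stop rate and any link between stopping and benefit are assumptions. With about one participant stopped in 24, the effect on type I error is slight (5.3% to 5.8% at correlations of 0.3 to 0.5). With 10% stopped it is modest (5.8% to 7.3%, bias 0.35 to 0.59 points against an SE of 1.22). With no correlation there is no bias, only a loss of power: at 10% stopped, from 90.7% to 87.9% if 6% is the SD of the difference, or from 80% to 76.1% if 24 gives exactly 80%. These results do not show that H4 will be overstated. They do show that the handling should be fixed before analysis, which costs little.

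**What to change.** Leave all safety rules unchanged. Whether any walking test follows a stop is for the investigators to state; Section 7 needs only to say how the resulting session is treated. In Section 7 (H4):

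1. Replace the repeated measures ANOVA with a linear mixed model, strategy as fixed effect and participant as random effect, fitted to all sessions that have a within-session score.
2. Report, for each strategy, the number of sessions ended by the blood pressure rule and, separately, the number interrupted by the heart rate rule.
3. For the propulsion contrast only, add a supportive sensitivity analysis over a range of assumed values for unscored stopped sessions, with zero change as one extreme. Its significance should not be a condition for supporting H4.

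The cost is a few sentences in Section 7, two counts per strategy and one extra analysis. The events are already observed through the monitoring in Section 5, although they would need to be recorded by strategy. The limit of the remedy should be stated as well: the mixed model keeps completed sessions and recovers some precision, but it does not remove bias if stopping depends on the response that was not observed. Items 2 and 3 let a reader judge that risk.
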